9.3 Analysis Populations

Approximately 25 older adults (aged 50-89 years) are expected to be enrolled in this Phase II trial to evaluate longitudinal findings from multimodal MRI.

Populations to be analyzed in the study include the Full Analysis Population (all participants who received any study drug and who participated in at least one post-baseline assessment), Per Protocol Population (all participants who adhere to the major

criteria in the protocol and who did not substantially deviate from the protocol), Safety Population (all participants who received any study drug, excluding participants who drop out prior to receiving any study drug). Evaluable participants (those with baseline and completed follow-up data) will be included in final statistical analyses.

Data may be excluded from analysis on the basis of participant non-compliance with the protocol. Outliers will be identified by testing including Pierce's Criterion, Chauvenet's Criterion, Grubb's test for outliers, and Dixon Q's test. If necessary to address outliers, the statistician will employ standard Winsorization techniques.

The primary analysis model for the efficacy endpoints will be an MMRM analysis. All available data will be included in these models with no imputation for missing data. Supportive analyses of efficacy data may be conducted to evaluate different methods of handling missing data (i.e., Last Observation Carried Forward, Baseline Observation Carried Forward, multiple imputation for missing data, etc.).

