5.8 Treatment Compliance

Participants / primary caregiver / study partner will be instructed to bring their unused investigational product (IP) to every visit. Compliance will be assessed by capsule counts. Details will be recorded in the case report form. All unused IP will be collected from the participant at V10/ET. Noncompliance is defined as taking less than 80% or more than 120% of the assigned dose during any outpatient evaluation period (visit to visit). Discontinuation for noncompliance is at the Investigator's discretion.

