9 PLANNED STATISTICAL METHODS

9.1 General Considerations

Statistical analyses will be performed by the statistician on staff with The Regenesis Project. Software for statistical analyses will include Microsoft Excel (version 14 or newer) and IBM SPSS Statistics for Windows, version 26 (IBM Corp., Armonk, N.Y., USA). Statistical analyses will be run to compare change from baseline at the post-intervention termination follow-up (three months after baseline) using a level of significance of 0.05.

A single unblinded interim analysis may be performed when 30% to 50% of the participants have completed the final follow-up timepoint. The purposes of this interim analysis are to declare futility, study discontinuation for overwhelming efficacy, or sample size re-estimation. The sample size will not be reduced based on interim data.

The primary analysis model for the efficacy endpoints will be an MMRM analysis. All available data will be included in these models with no imputation for missing data. Supportive analyses of efficacy data may be conducted to evaluate different methods of handling missing data (i.e., Last Observation Carried Forward, Baseline Observation Carried Forward, multiple imputation for missing data, etc.). These supportive analyses will be detailed in the SAP. Each endpoint within the neuropsychological testing family will be analyzed using MMRM analysis methods in a similar manner as to how the primary endpoints will be analyzed. Formal significance for a given hypothesis will only be declared if that hypothesis is significant and all hypotheses within the family preceding it are significant. This approach will ensure strong type 1 error control is present for all statistical tests conducted.

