10.8 Protocol Violations/Deviations

Deviations from the protocol which will be considered protocol violations include late “out-of-window” follow-up telephone and in-person visits and missed testing appointments. These deviations will be reported in the final clinical study report.

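### Section 9.3 lets data be excluded for protocol non-compliance without criteria, timing or a named population, and the primary analysis population is never stated

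*Combined protocol and SAP*

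**What the plan says.** Section 9.3 defines a Full Analysis Population (any study drug and at least one post-baseline assessment), a Per Protocol Population and a Safety Population. Per Protocol membership requires adherence to the major "criteria in the protocol and who did not substantially deviate from the protocol"; neither the major criteria nor substantial deviation is defined. Three further rules follow in the same section:

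- On exclusions: "Data may be excluded from analysis on the basis of participant non-compliance with the protocol". This sentence comes after the populations have been defined and is not attached to any of them.
- For the primary model: "All available data will be included in these models with no imputation for missing data". Section 9.1 repeats this and states "The primary analysis model for the efficacy endpoints will be an MMRM analysis".
- On who enters the final analyses: "Evaluable participants (those with baseline and completed follow-up data) will be included in final statistical analyses".

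Two other sections bear on what non-compliance could mean. Section 5.8 has the only numerical definition: "Noncompliance is defined as taking less than 80% or more than 120% of the assigned dose", judged from visit to visit by capsule count. Section 10.8 counts as violations out-of-window "follow-up telephone and in-person visits and missed testing appointments", with no minor and major tiers, and says that these will be reported in the study report. Section 9.3 cites neither section.

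On design, Section 5.1.2 provides no placebo group and Section 5.5 no blinding. Section 9.1 gives the analysis to the statistician on the site's staff and allows one unblinded interim analysis once 30% to 50% of participants have finished follow-up.

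**The concern.** A discretionary exclusion rule is harmless if its criteria are fixed before anyone sees results, or if it affects only a secondary analysis set. Section 9.3 secures neither. The same staff know the treatment, collect the outcomes, record the deviations and analyse the data, and no step is described that settles exclusions before outcomes are read. With no control arm, removing participants who did badly moves the estimated change directly, because no second arm is subject to the same rule.

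Intent is not needed for this to happen. In a dementia population, a participant who is declining may plausibly also miss capsules or appointments, so exclusion for non-compliance can track outcome by itself. About 20 completers are planned, so one to three exclusions are enough to matter.

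**Working it through.** **1. The plan's own figure.** Section 9.2 enrols 25 to obtain 20 completers with 20% attrition: 20 / (1 − 0.20) = 25. This reproduces. The 20 itself cannot be rebuilt, because no effect size, SD, endpoint or sidedness is given. A paired t-test with n = 20, 80% power and two-sided 0.05 corresponds to a standardised change of 0.66.

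**2. The rules side by side.** Take a participant with baseline and follow-up scans and a logged violation. Under the all-available-data rule and under the evaluable rule the participant is in; under the exclusion sentence the participant may be out. Now take one who stops early but has the scan that Section 7.4 offers at early termination. That participant has available data and is in the Full Analysis Population, but may not count as having completed follow-up. The text does not say which rule governs the primary analysis in either case.

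**3. How many participants could have a violation.** Section 7.3 schedules a call within 24 hours, weekly calls, a week-1 visit and monthly visits. Counted over three months, that is 13 to 14 calls and 4 visits, so m = 17 to 18 contacts. The documents give no lateness rate. Assuming a probability p of lateness per contact, independent across contacts, P(at least one) = 1 − (1 − p)^m:

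| p | Share with a violation | Of 25 |
|---|---|---|
| 1% | 16–17% | about 4 |
| 2% | 29–31% | 7–8 |
| 5% | 58–60% | about 15 |
| 10% | 83–85% | about 21 |

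**4. Effect on error if exclusions follow outcome.** Simulation of 200,000 trials with no true effect: n = 20 normal change scores, T = mean / (s / √n) on the participants kept, two-sided 0.05. The entries are the chance of a significant benefit, with the shift in mean change in SD units in brackets. With nobody removed the chance is 2.6%, against a nominal 2.5%.

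| Open to exclusion | Worst 1 removed | Worst 2 removed | Worst 3 removed |
|---|---|---|---|
| All 20 | 7.6% (0.10) | 15.6% (0.18) | 26.0% (0.26) |
| 10 of 20 | 6.1% (0.08) | 9.8% (0.14) | 12.9% (0.19) |
| 5 of 20 | 4.8% (0.06) | 5.8% (0.09) | 5.5% (0.10) |

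Counting both tails, the first row is 8.9%, 16.3% and 26.3%.

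**5. Exclusions unrelated to outcome.** Removing one to three participants at random leaves two-sided error at 0.050 to 0.051. The cost is then power only: at a standardised change of 0.66, 80% with 20 participants, 75% with 18, 70% with 16 and 66% with 15.

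**The case against.** The best defence is that the exclusion sentence was meant for the Per Protocol Population. That definition already has a severity threshold, which suggests that trivial deviations were not meant to remove anyone. On this reading the tension largely disappears. It is plausible, but the text does not say so; if it was the intent, the fix simply records it.

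Four stronger readings are tempting, and the documents do not support them.

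- *A late telephone call gets a participant excluded.* Section 9.3 does not cite Section 10.8, and Section 10.8 prescribes only reporting. The calls are made to participants, so a late one may be the site's deviation rather than participant non-compliance. What stands is that nothing in Section 9.3 rules exclusion out.
- *Almost any participant could be removed.* No lateness rate is given, and only about 10% lateness per contact approaches that.
- *Section 9.3 flatly contradicts itself.* The all-available-data sentence introduces the missing-data alternatives, and can be read as a missing-data rule applied after the analysis set is chosen. That makes it ambiguous rather than contradictory.
- *Removing a few poor responders creates a drug effect.* Even with the three worst of 20 removed, 1 − 0.26 = 74% of null trials show no significant benefit.

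The top row of the table in step 4 is also an extreme case: everyone is open to exclusion and the worst are picked perfectly. The t-test is the plan's test for secondary endpoints (Section 9.5.2). Glutathione, a primary endpoint, is assigned a Wilcoxon signed-rank test in Section 9.5.1, for which these exact figures do not apply.

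**Conclusion.** The concern holds in this form: the plan contains an open-ended exclusion rule, does not name the primary analysis population, and has no safeguard that fixes exclusions before outcomes are known. Outcome-related exclusion is a possibility the wording leaves open. It is not something the plan says will be done.

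If it occurred, the chance of a false significant benefit would rise from a nominal 2.5% to about 5–6% with 5 of 20 participants open to exclusion, about 6–13% with 10, and 7.6–26% with all 20. These figures assume n = 20, normal change scores, a t-test at two-sided 0.05, one to three removals and removal of the worst among those eligible. The sizes are illustrative. The gap in the wording does not depend on them. This is a cheap improvement.

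**What to change.** In protocol Section 9.3, and in the separate SAP that Section 9.1 mentions:

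1. State that the primary efficacy analysis uses the Full Analysis Population, with no exclusion for non-compliance.
2. Delete the evaluable-participants sentence or reconcile it with item 1, including how early-termination assessments are used. Without this, Section 9.3 would still hold two competing rules.
3. Move the exclusion sentence into the Per Protocol definition and make that analysis a sensitivity analysis. Tie it to the 80–120% capsule count in Section 5.8, saying whether one non-compliant period is enough, and to a list of major deviations that separates the violations in Section 10.8 into major and minor.
4. Fix and date that list before any follow-up outcome data, including interim data, are read.
5. Report every exclusion with its reason, and the result with and without it.

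The cost is a wording change to the protocol and SAP; no participants, visits or procedures are added. The small downside is that the primary estimate will include less compliant participants and may be slightly diluted. The Per Protocol sensitivity analysis would show by how much.

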9.2 Determination of Sample Size

Approximately 25 participants are expected to be enrolled in this Phase II trial to evaluate longitudinal findings from multimodal MRI among the population that is being studied. The study population is sufficiently broad and the conditions of interest are sufficiently prevalent so that recruitment of participants is not a limiting factor for the trial site.

The sample size was chosen according to a power analysis calculated with 80% power and a significance level of 0.05. To achieve completion data for at least 20 participants, enrollment of 25 participants will allow for 20% attrition while maintaining statistical integrity.

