9.5.1 Statistical Analysis for Primary Imaging Endpoints

Repeated Measures ANOVAs (RMANOVAs) will be employed to evaluate whether the participants who successfully complete the treatment protocol demonstrate differential improvement in cognition over time with global and domain level mean T-scores as the outcome variable of interest. The same ANOVA-based statistical analysis paradigms will be applied to the neuroimaging data after it is preprocessed. RMANOVAs will be run to determine whether the treatment group demonstrated improvements in the below imaging modalities, from baseline to study completion. Age, sex, and education, as statistically indicated, will be included as additional regressors. Correlation analyses will then be conducted to determine whether absolute change in domain level as measured by neuropsychological evaluation and global cognitive performance is associated with absolute change in the following imaging parameters. To compare individuals from the study population with a “normal” population, Z-score will be calculated for each individual for each component of the toolbox as well as compute a global-cognitive Z-score metric. This will allow the comparison of individual participants to a large population of normal derived from the published literature (e.g. Human Connectome Project).

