9.5.2 Statistical Considerations for Secondary Endpoints

Secondary endpoints will include a longitudinal comparison of metabolic and serological analysis (specifically measures of glucose and insulin homeostasis); the level of cognitive impairment as defined by neuropsychological testing (QDRS/CDR, MMSE, ADAS-Cog, and MoCA scores). Thresholds for reporting clinically meaningful change will include references to published minimal clinically important differences (MCIDs) for each measure. Paired samples t-tests will be used to statistically analyze each secondary endpoint, including the cognitive measures described below as well as changes in serological markers.

The ADAS-Cog evaluates participants' cognitive abilities. It is composed of 11 parts that measure word recall, object/figure naming, command following, constructional praxis, ideational praxis, orientation, word recognition, test direction recall, spoken language, comprehension, and word-finding difficulty. The ASAS-COG is scored from 0-70 by measuring the errors made in each task, with a score of 70 representing the most severe impairment. A point reduction of 3.1 to 3.8 has been found to be the minimal clinically important difference (Schrag & Schott, 2012).

The MMSE is a 30-point questionnaire that evaluates cognition. The MMSE includes specific tasks that assess orientation, attention, memory, language and visual-spatial skills. MMSE scores range from 0 – 30 possible points; 0-17: severe cognitive impairment, 18-23: mild cognitive impairment, 24-30: no cognitive impairment. A point decrease \geq 3 on the MMSE has been identified as the minimally clinically important difference (Andres, 2019).

The MoCA evaluates frontal-executive functions (e.g., verbal abstraction and mental calculation), language (e.g., confrontation naming, phonemic fluency), orientation (e.g., person, place, date, day of the week, and time), visuospatial construction (e.g., simple figure copy), divided visual attention, and immediate and delayed memory of unstructured information (Nasreddine, Phillips, Bédoré, Charbonneau, Whitehead, Collin, et al., 2005). MoCA scores range from 0-30 possible points; 26 or greater is considered to reflect normal cognitive status.

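### The outlier rule in 9.3 is open-ended: depending on how its four tests combine, it flags about 3% to 36% of clean variables, and Winsorizing those makes ordinary tests understate the standard error

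*Combined protocol and SAP*

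**What the plan says.** Section 9.3 deals with identification first: "Outliers will be identified by testing including Pierce's Criterion, Chauvenet's Criterion, Grubb's test for outliers, and Dixon Q's test". The list is open. The section gives no level for the tests, no standard-deviation convention, no Dixon variant and no rule for when the tests disagree. It does not say whether baseline, follow-up or change values are screened. Handling follows: "If necessary to address outliers, the statistician will employ standard Winsorization techniques". No trigger or limits are given, and results without the alteration need not be reported.

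Three kinds of ordinary analysis could receive altered values. Section 9.3 says "The primary analysis model for the efficacy endpoints will be an MMRM analysis". Section 9.5.1 says "RMANOVAs will be run to determine whether the treatment group demonstrated improvements in the below imaging modalities, from baseline to study completion". Section 9.5.2 says "Paired samples t-tests will be used to statistically analyze each secondary endpoint". Section 9.5.1 also assigns a signed-rank test to NAA:Cr and to glutathione. The documents describe no variance or degrees-of-freedom adjustment for Winsorized data.

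There is no control group (5.1.2) and no blinding (5.5), and the analyst is the sponsor's staff statistician (9.1).

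**The concern.** An outlier test should ask whether a value is too extreme to belong with the rest, at a known error rate. Grubbs' and Dixon's tests can be run that way. Chauvenet's criterion puts its limit where half an observation per sample is expected by chance, and Peirce's limit is slightly lower still at these sample sizes. Both therefore often flag the largest value of a perfectly good sample. With no combining rule, which criterion governs is decided after the data are seen.

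Winsorizing then pulls in the tails, and an ordinary test treats the altered values as raw data. The sample variance shrinks more than the true variability of the mean does, so the standard error is too small. At stake are genuine large changes in either direction, and the claim in 9.1 that the testing approach strongly controls Type I error.

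**Working it through.** **Inputs.** From the plan: 20 completers of 25 enrolled with 20% attrition (9.2), significance level 0.05 (9.1), the four tests (9.3), and the models in 9.3, 9.5.1 and 9.5.2. Assumed: Grubbs and Dixon at two-sided 0.05, SD with divisor n − 1, Peirce's limit for one doubtful value, screening of change scores, and clean normal data.

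**1. The plan's own figure.** 20 / (1 − 0.20) = 25, as in 9.2. The 20 cannot be checked, because no effect size or SD is given. By noncentral t, a two-sided paired t-test has 80% power for a standardized change of 0.66 at n = 20 and 0.58 at n = 25. The plan states no false-flag rate to compare with what follows.

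**2. Limits on max |x − mean| / SD (n = 20; n = 25).**
- Chauvenet, z(1 − 1/(4n)): z(0.9875) = 2.241; z(0.99) = 2.326. Expected count beyond the limit: n × 2 × 1/(4n) = 0.5.
- Peirce: 2.209; 2.307.
- Grubbs, (n − 1)/√n × √(t²/(n − 2 + t²)), with t the upper 0.05/(2n) point on n − 2 df: 2.708; 2.822.
- Dixon: cut-off calibrated by simulation to 5%.

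Rough check: with known mean and SD, the chance that at least one of 20 values passes Chauvenet's limit is 1 − 0.975^20 = 0.40. Estimating both from the same sample lowers this to 0.33.

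**3. Flag rates, 400,000 clean normal samples at each n.**

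| Rule | n = 20 | n = 25 |
|---|---|---|
| Peirce | 36.1% | 35.6% |
| Chauvenet | 32.6% | 33.6% |
| Grubbs | 5.0% | 5.0% |
| Dixon | 5.0% | 5.0% |
| Any one of four | 36.1% | 35.6% |
| At least two | 32.6% | 33.6% |
| At least three | 6.8% | 6.7% |
| All four | 3.2% | 3.2% |

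The any-test rate equals Peirce's because Peirce has the lowest limit; Grubbs and Dixon add almost nothing.

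**4. Across the five primary endpoints in 2.1.** Take one independent variable each and the any-test rate of 0.36. The expected number flagged is 5 × 0.36 = 1.8. The chance of at least one flag is 1 − 0.64^5 = 0.89, and of all five 0.36^5 = 0.006.

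**5. Type I error.** With two time points, complete data and no covariates, RMANOVA and MMRM reduce to the paired t-test. So a one-sample t-test on change was simulated with no true change, Winsorizing every sample flagged under the any-test reading (400,000 samples; n = 20 / n = 25).

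| Winsorizing | Type I error | Estimated SE ÷ true SD of mean | Type I error, flagged variables only |
|---|---|---|---|
| None | 5.0% / 5.0% | 1.00 / 1.00 | 5.0% / 5.0% |
| Clip to flag limit | 5.3% / 5.2% | not computed | not computed |
| To nearest unflagged value | 6.6% / 6.1% | 0.95 / 0.96 | 9.3% / 8.2% |
| One value per tail | 6.7% / 6.3% | 0.94 / 0.96 | 9.8% / 8.6% |
| Two values per tail | 8.7% / 7.6% | 0.90 / 0.92 | 15.2% / 12.5% |

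A separate run of 200,000 samples reached 5.5% for clipping, 6.9% for nearest value or one per tail, and 8.9% for two per tail. The ranges quoted cover both runs. The unaltered test stays at 5% in flagged variables, so the excess comes from the Winsorizing.

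**6. Signed-rank test.** Nearest-value Winsorizing moves its rejection rate from 4.8% to 5.5% (n = 20) and from 4.6% to 5.0% (n = 25).

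**The case against.** **The 36% is one reading, not the plan's rate.** This stands. A reader might infer that silence on disagreement means any single flag counts. Section 9.3 does not say so, and if three or all four tests must agree the rate is 7% or 3%. But it contains no agreement requirement either, and requiring two still leaves 33–34%.

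**Flagging is not altering.** This also stands. Winsorizing is discretionary, so the Type I figures show what happens if every flagged sample is Winsorized. Under the mildest form the effect is negligible. If each visit is screened separately (correlation 0.5–0.9 assumed), 50–59% of variables are flagged. Type I error is then 5.2–6.3% for clipping, nearest value or one per tail, and 6.1–7.5% for two per tail.

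**Not all primary results are exposed.** One might infer that nearly every primary endpoint will have flagged values. With one variable each, the expected number is 1.8 of 5, and 89% is only the chance of at least one. Seven independent variables, the number of DTI and NODDI metrics in 9.5.1, would give 1 − 0.64^7 = 96%, but correlation lowers that. Glutathione and NAA:Cr go to a signed-rank test, which uses no estimated standard error. The plan does not say how a scalar screen would apply to voxel-wise DTI and ASL maps.

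**Direction.** One might infer a tilt towards the drug. Winsorizing applied to both tails pulls in the best responders as readily as the worst decliners, and nothing in 9.3 says only decliners would be altered. Selective use would matter: pulling in only a flagged worst decliner raises one-sided false improvement from 2.5% to 3.4% (n = 20) or 3.1% (n = 25). The plan does not prescribe that.

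**Sample size.** The one-third rate belongs to samples near 20–25. Chauvenet's criterion flags about 13% at n = 5, 27% at n = 10 and 38–39% at n = 500.

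**Conclusion.** The point holds in limited form. It is more than missing detail, because two of the four named criteria are not tests at a controlled level, and the altered data would enter tests that take no account of the alteration. The overall inflation is modest, but it is larger in the variables actually flagged. It concerns scalar outcomes analysed by RMANOVA, MMRM or paired t-test, not the signed-rank endpoints. Depending on the unstated Winsorizing limits, the effect ranges from trivial to a nominal 5% test running near 9%.

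These sizes rest on the assumptions listed in the working. Two of them matter most. An n-divisor SD would raise Peirce's rate to 42.7% (n = 20) and 40.8% (n = 25). Heavier tails would raise the any-test rate further, to 66% and 70% for a t distribution with 4 degrees of freedom. The documents do not support a claim that the plan will flag a third of its variables or that its primary results are generally invalid.

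**What to change.** In 9.3, make the analysis of values as recorded the main analysis, and delete the four-test screen and Winsorization from it. Allow a value to be corrected or removed only for a documented technical fault (failed scan quality control, laboratory error or transcription error), decided without knowledge of the time point. Handle extreme values in a named sensitivity analysis. This can be the signed-rank test already used in 9.5.1, or Yuen's trimmed-mean test with its matching Winsorized-variance standard error.

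A lesser repair, if a screen is wanted, is one Grubbs test at 0.05 on a stated variable with stated Winsorizing limits. It flags 5% of clean variables and holds Type I error to about 5.1–5.5% (5.5–5.8% with two per tail).

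The cost is wording only, with no added participants, visits or data. The downside is that a genuinely aberrant value stays in the main analysis and may widen its interval; the sensitivity analysis will show how much it matters.
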